5.8 Laboratory results

Laboratory results (haematology, biochemistry and urinalysis) will be presented in data listings as an appendix to the CSR. Any significant out of range values are captured as AEs and will be presented in the summary AE tables (see Section 5.7).

5.8.1 Additional safety tables

A table of ISR grade by vaccination number will be produced.

CRUKD/17/003 RAP Version: 2.0 09Mar2023 FINAL

Table 12: Summary of Injection Site Reactions by Grade and Vaccination Number (*Safety Population*)

ISR Grade	Vaccination number at onset						
	Total	1	2	3	4	5	6
1	N	N	N	N	N	N	N
2							
3							
4							
5							

5.8.2 Stopping rule criteria

Any AEs that meet the stopping rule criteria will be presented descriptively.

5.9 Efficacy

Documentation of tumour response is a secondary objective of this trial. Anti-tumour activity will be measured according to the modified irRC; (see Protocol Appendix 3) at 30 days (+/- 5 days) after the last AST-VAC2 vaccination in all patients. The overall response will be presented for the 'Response Population' (see Table 13).

The response rate is defined as the ratio of patients with any response (immune-related complete response [irCR] or immune-related partial response [irPR]) to the total number of patients included in the efficacy population.

Overall survival will be assessed in the 'Safety Population' and is defined as the time from the first AST-VAC2 vaccination to the date of death (regardless of whether the patient went on to receive other anti-cancer treatments) or date of last contact (if patient is still alive or lost to follow-up). Survival will be summarised for each patient as shown in Table 14. Patients with data censored for survival will be indicated with a '+' after the number of days.

CEA data will be listed per patient.

Table 13: Overall Response (*Response Population*)

Overall Tumour Response	No. of Patients N=XX
irCR	X (XX.X%)
irPR	
irSD	
irPD	
NE	
Response rate (irCR + irPR)	

Table 14: Summary of Survival (*Safety Population*)

Patient	Time to Death (or Last Contact) (days)
XX/XXX	N
XX/XXX	
XX/XXX	
XX/XXX	
Median (range)	X (X-X)

Table 15: Two Year Survival (*Safety Population*)

Patients alive	Patients deceased
N (%) [XX/XXX, XX/XXX...]	N (%) [XX/XXX, XX/XXX...]

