**13.6 Tumour response**

Disease assessment will be performed at baseline and following completion of the vaccination schedule for measurement of potential responses to trial treatment. Patients who receive at least one vaccination and have both a baseline and at least one repeat assessment, will be evaluable for response.

Objective responses and the best tumour response achieved by each patient while on trial and overall survival will be described and presented in data listings.

Overall survival data will continue to be collected (at those time points noted in [Section 7.4](#)) for up to two years after the first vaccination for all patients or until all patients have died, according to whichever event occurs first.

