4.1 Patient Populations

The analysis sets are defined as follows:

Full Analysis Population (FAP): All patients who enrolled onto the main trial.
Patients who are enrolled in error onto the main trial (due to ineligibility/administrative error), prior to receiving any AST-VAC2 vaccinations, will be excluded from the FAP.

Safety Population: All enrolled patients who received at least one AST-VAC2 vaccination.
This population will also be used for overall survival at 2 years post first AST-VAC2 vaccination. Patients are evaluable for survival regardless of whether they go on to receive another anti-cancer therapy.

HLA Population: All patients who had a sample taken for HLA analysis.
[Redacted]

Secondary Immunogenicity Endpoint Population: All eligible patients who received at least three AST-VAC2 vaccinations and have had a baseline blood sample and at least two post-vaccination blood samples taken.
[Redacted]

Response Population: All eligible patients who have received at least one AST-VAC2 vaccination and have had a baseline assessment of disease and at least one repeat disease assessment measured according to irRC. For details of irRC, refer to Appendix 3 of the study protocol.
If rapid tumour progression occurs before completion of the scheduled six AST-VAC2 vaccinations, the patient will be classified as having early progression. Patients with early progression will be included in the response population.

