To determine the immunogenicity (peripheral response) of AST-VAC2	Observation of the total number of patients showing durable peripheral immune response, defined as a change in one validated assay at two time points after at least two vaccinations.	
Measure Title: Number of Participants Showing a Durable Peripheral Immune Response
 
Measure Description: Immunological response in whole blood (peripheral blood mononuclear cells) by human telomerase reverse transcriptase (hTERT) specific T cells measured by enzyme-linked immunospot (ELISPOT), with a durable peripheral immune response defined as a change in one validated assay at two time points after at least two vaccinations (where a change is defined as 2.5 fold change over baseline [after removal of background], assay control and >35 spots/10⁶ cells).
 
Time Frame: Screening, vaccination weeks 3, 4 and 6; 2 weeks post last vaccination and 3, 6 and 12 months post first vaccination.
 
Measure Type: Count of participants
 
Measure of dispersion/precision: Not applicable
 
Measure Title: Mean Fold Change in hTERT Specific T Cells Over Baseline by Timepoint
 
Measure Description: Immunological response in whole blood (peripheral blood mononuclear cells) by hTERT specific T cells measured by ELISPOT and presented as mean fold change in spots/10⁶ cells (after removal of background) from baseline to each timepoint assessed.
 
Time Frame: Screening, vaccination weeks 3, 4 and 6; 2 weeks post last vaccination and 3, 6 and 12 months post first vaccination.
 
Measure Type: Mean
 
Measure of dispersion/precision: Full range

To document any tumour response(s) in patients receiving the AST-VAC2 vaccine.	Re-assessment of tumour size at end of vaccination visit with MRI or CT using Immune-Related Response Criteria (irRC).	
Measure Title: Tumour Response According to Immune-Related Response Criteria (irRC) Post Vaccination
 
Measure Description: Number of participants with complete response, partial response, stable disease, progressive disease or who

		
were not evaluable at radiological disease assessment (computerised tomography and/or magnetic resonance imaging) at the End of Vaccination visit according to irRC (Appendix 3 of protocol).
 
Time Frame: Baseline to End of Vaccination visit (30 days post last vaccination).
 
Measure Type: Count of participants
 
Measure of dispersion/precision: Not applicable

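### The response rate in SAP 5.9 is divided by an efficacy population that is not defined, and the Response Population probably meant can lose some vaccinated patients who were never rescanned, which can raise the rate but not lower it

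*SAP*

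**What the plan says.** **Denominator.** SAP 5.9 counts patients with irCR or irPR and relates them "to the total number of patients included in the efficacy population". SAP 4.1 defines, in its readable text, a Full Analysis, a Safety, an HLA, a Secondary Immunogenicity Endpoint and a Response Population, but no efficacy population. SAP 5.9 says just before the rate definition that overall response is presented for the Response Population, and the title of Table 13 repeats this.

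**Response Population.** Under SAP 4.1 its members are eligible, have had at least one vaccination, and "have had a baseline assessment of disease and at least one repeat disease assessment measured according to irRC". Protocol 13.6 has the same rule: "Patients who receive at least one vaccination and have both a baseline and at least one repeat assessment, will be evaluable for response". Protocol 3.4.1 and 10.2 agree.

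**Early progression.** SAP 4.1 adds: "If rapid tumour progression occurs before completion of the scheduled six AST-VAC2 vaccinations, the patient will be classified as having early progression". It continues: "Patients with early progression will be included in the response population". It does not say whether such a patient also needs a repeat scan.

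**Timing.** SAP 5.9 places the response assessment "at 30 days (+/- 5 days) after the last AST-VAC2 vaccination in all patients". Protocol 7.3.2 leaves later imaging to standard practice.

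**Outputs.** Table 13 has rows for irCR, irPR, irSD, irPD, NE and the response rate. Outcome Measure 5 (SAP 7.5 and 7.5.5) is a count: "Number of participants with complete response, partial response, stable disease, progressive disease or who" could not be evaluated. Neither output has an early-progression row, and the SAP does not define NE.

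**The concern.** A programmer cannot tell from the definition which patients belong in the denominator of a reported rate. If the Response Population is meant, membership depends partly on something that happens after treatment starts, namely whether a repeat scan was obtained. In advanced NSCLC the patients who miss that scan are likely to be those doing badly, and they cannot be responders. Leaving them out gives a rate among patients who reached a scan, which can be more favourable than the rate among patients who were vaccinated.

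The tables do not settle the matter. They have an NE row, but the obvious NE patients, those with no repeat scan, are outside the population tabulated. Early progressors are inside it but have no row of their own. At stake is the reading of one secondary endpoint, tumour response, in a trial of about eight patients.

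**Working it through.** The plan states no response rate, target or power, so there is no figure to reproduce. The check has two parts.

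**1. Who leaves the denominator if the Response Population is used?**

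| Vaccinated patient with no post-baseline scan | Kept under SAP 4.1? |
|---|---|
| Rapid tumour progression before six vaccinations | Kept by the early-progression sentence, though the SAP does not say whether a scan is also needed |
| Death or decline not classed as rapid tumour progression | No |
| Event after the sixth vaccination and before the scan | No |
| Withdrawal before the scan | No |

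For a patient who completes the schedule, the scan falls about 5 × 7 + 30 = 65 days after the first vaccination, so the third row covers a gap of about 30 days.

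**2. How far can the rate move?**

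Inputs:
- n = 8 vaccinated. This is an assumption; SAP Table 1 says approximately eight patients.
- r = responders (assumed 0, 1 or 2).
- k = vaccinated patients with no post-baseline scan (assumed 1 to 3).
- e = those of the k who are early progressors and are kept (assumed 0 to k).
- All eight are taken to be eligible. The Response Population is limited to eligible patients and the SAP's Safety Population is not, which is a separate difference.

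Formulas:
- Rate over all vaccinated patients: r / 8.
- Rate over the Response Population: r / (8 − k + e).

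An unscanned patient adds nothing to r, and e cannot exceed k. The second rate is therefore never below the first.

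With no early progressors among the unscanned (e = 0):

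| Responders | All vaccinated | k = 1 | k = 2 | k = 3 |
|---|---|---|---|---|
| 0 | 0/8 = 0% | 0/7 = 0% | 0/6 = 0% | 0/5 = 0% |
| 1 | 1/8 = 12.5% | 1/7 = 14.3% | 1/6 = 16.7% | 1/5 = 20.0% |
| 2 | 2/8 = 25.0% | 2/7 = 28.6% | 2/6 = 33.3% | 2/5 = 40.0% |

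Effect of keeping early progressors, with r = 1 and k = 3:

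| e = 0 | e = 1 | e = 2 | e = 3 |
|---|---|---|---|
| 1/5 = 20.0% | 1/6 = 16.7% | 1/7 = 14.3% | 1/8 = 12.5% |

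If every unscanned patient is a retained early progressor, the two rates are the same.

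**The case against.** The other side has a good case. The Response Population is very probably what SAP 5.9 means, since the sentence before the definition and the table title both say so. A set of patients evaluable for response is the protocol's own rule, and the SAP follows it. Protocol 10.1 expects every vaccinated patient to be assessed after the last vaccination, so missing scans should be few. The objective is only to document responses. SAP 7.6 plans no statistical analysis of the secondary endpoints, and response is not among the factors for further development in Protocol 13. SAP 5.1 details exclusions from each population and SAP 6.1 lists responses by patient, so a reader can recompute the rate. All of this stands, and it limits the weight of the point. It does not define the denominator or put the unscanned patients back into it.

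Several stronger readings are tempting, but the documents do not support them.

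- A reader might infer that every patient without a post-baseline scan is dropped. SAP 4.1 expressly includes early progressors, who are a main group likely to miss the scan.
- A reader might infer that each patient must stay well for about nine weeks to be counted. That holds only for those who complete six vaccinations. Under Protocol 5.4, a patient who stops early has the End of Vaccination visit within 30 days of the last vaccination or when the decision to withdraw is taken. After two vaccinations that is at most about 7 + 30 = 37 days after the first.
- A reader might apply the 32% one-year survival in Protocol 2.1.1 at a constant hazard: 1 − 0.32^(65/365) = 18%, or about 1.5 of 8 dead before the scan. That is a background lung-cancer figure. Protocol 4.1.1 requires a life expectancy of at least 12 weeks (84 days) and patients likely to be well enough for six vaccinations, so 18% is not an estimate for this trial.
- A reader might infer that the NE row must stay empty. NE is undefined and could hold an unusable repeat scan or an early progressor without a scan.
- A reader might carry the rate shift over to Outcome Measure 5. That measure reports counts, and dropping an unscanned patient leaves the responder counts unchanged.

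**Conclusion.** The point holds in a limited form. The denominator in SAP 5.9 refers to a population that the readable SAP does not define. Under the most likely reading, vaccinated patients without a repeat scan who are not classed as early progression leave the denominator, and the rate can then only rise or stay the same.

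With 8 vaccinated, the rise is 1.8, 4.2 or 7.5 percentage points for 1 responder and 1, 2 or 3 patients dropped. For 2 responders it is 3.6, 8.3 or 15.0 points. It is zero with no responders, or when all unscanned patients are retained early progressors. For scale, the exact (Clopper-Pearson) 95% interval for 1/8 runs from 0.3% to 52.7%, so the shift is small against the uncertainty of the rate.

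These sizes rest on assumed numbers of responders and missing scans, since the documents give neither. Parts of SAP 4.1 are blacked out in the public copy, so a definition there cannot be fully excluded. The readable contents and table list name no efficacy population. SAP 6.1 uses an appendix heading for patients excluded from efficacy analysis but does not define the set.

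The endpoint is secondary and descriptive, with no test or threshold. The point is minor, but cheap to put right.

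**What to change.** 1. In SAP 5.9, replace the efficacy population with named sets from SAP 4.1.
2. In Table 13, report the response rate over all vaccinated patients (Safety Population). Put patients with no post-baseline scan in the NE row and count them as non-responders. Keep the protocol-defined Response Population rate in the column beside it.
3. In SAP 4.1, state whether an early progressor needs a repeat scan to be included, and state which row of Table 13 and of Outcome Measure 5 takes an early progressor without one.
4. In Outcome Measure 5, show the other unscanned vaccinated patients as NE, so that the number analysed covers everyone vaccinated.

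The cost is SAP wording, one extra column, and a rate that may look less favourable. No new data are needed, and the protocol's evaluability rule is still reported.

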### 13.1 Interim analysis

An interim analysis will be conducted once all patients administered AST-VAC2 have withdrawn, died or completed their two-year follow-up visit for survival.

Once this condition is met, a data cut-off will be established. All patient visits occurring on or before this date will be analysed and summarised in the clinical study report including safety data to date and assessment of overall survival at two years.

Any data collected after this date will be summarised in a supplemental report produced for the final analysis to satisfy the safety reporting requirements for AST-VAC2 as an ATIMP.

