5.10 General data conventions

There is only one dose level for this study, as specified in the study protocol. Patients who deviate from the assigned dose and/or schedule will be clearly described in the CSR with regards to their treatment modification and if applicable in the list of protocol deviations (Section 5.4).

Continuous variables will be summarised and presented with summary statistics.

The median OS will be presented.

Categorical variables will be summarised in frequency tables. Percentages in the summary tables will be rounded and may therefore not always add up to exactly 100%.

The convention in Rave is that an unknown day resolves to 1st of the month and an unknown month resolves to January. Dates may be ordered by this; however, CRUK do not perform calculations on unknown dates except as stated below.

Durations of AEs: the start date of an AE is considered as Day 1 of the event and should be included in all duration calculations (i.e. if an AE starts and stops on same day, the duration should be reported as one day).

- For unrelated AEs, those with missing or partially completed end dates will not be excluded from analysis and the duration of the AE will be calculated from the first day of the month (if unknown) or first day of the year (based on RAVE conventions).
- For related AEs, prior to final data lock, an end date will be either i) confirmed AE end date or ii) stabilisation of AE. Cases where this is not possible are if the patient was lost to follow up. If lost to follow-up then the AE would stay as not recovered/not resolved. In this case duration would not be calculated.

Time to onset of AEs from IMP administration: the time to onset should be calculated from the date of the first AST-VAC2 vaccination and AEs occurring within a specific vaccination window (e.g. start date from date of 2nd vaccination to before date of 3rd vaccination) should also have times to onset calculated from the date of the last vaccination administered in that window (e.g. Vaccination 2). Onset time will be

calculated as 0 if the AE occurs on the same day as the dose; however, if the start time is missing, onset time will not be calculated (only applicable when the drug admin has a start time entered).

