7.2 Participant Flow

The participant flow section of the results upload will include the following details. The programmed table output for reason not completed may be re-categorised to ClinicalTrials.gov categories and reviewed by Clinical Study Manager for approval.

Period Title	Overall Study
Arm/Group Title	Experimental: AST-VAC2
Arm/Group Description	Participants will receive up to a maximum of six vaccinations over six weeks. Each weekly AST-VAC2 vaccination will be administered as a split dose via two intradermal injections at a target dose defined as 1×10^7 viable cells. There is no dose escalation planned during the study; only one dose level will be explored.
	Number of Participants
Started (participants enrolled into main trial)	*
Completed (6 vaccinations)	
Not completed	
Reason not completed	
Adverse Event	
Death	
Lack of Efficacy	
Lost to Follow-up	
Physician Decision	
Pregnancy	
Protocol Violation	
Withdrawal by Subject	
Disease Progression	

Sponsor's decision to terminate the trial	
Started (participants entered follow-up period)	
Completed (2-year OS follow up)	
Not completed	
Reason not completed	
Lost to follow-up	
Withdrawal of consent	
Death	
Declined to attend follow-up visit	

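### SAP Table 14 names no censoring-adjusted estimator for median overall survival, and the two-year survival tables have no category for unknown status (minor)

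*SAP*

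**What the plan says.** **Median.** SAP 5.9 runs OS from first vaccination to death "or date of last contact (if patient is still alive or lost to follow-up". Table 14 holds both in one column, headed "Time to Death (or Last Contact) (days", and its last row is one median with a range. On censoring, 5.9 gives a display rule: "Patients with data censored for survival will be indicated with a" plus sign after the number of days. SAP 5.10 adds "The median OS will be presented" and no method. Neither document names Kaplan-Meier or any other censoring-adjusted estimator.

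**Two-year status.** The denominator is fixed. SAP 4.1 says of the Safety Population: "This population will also be used for overall survival at 2 years post first AST-VAC2 vaccination". Table 15 and Outcome Measure 6 (SAP 7.5.6) have two categories, alive and deceased.

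**Unknown status is foreseen.**
- Protocol 13.1 triggers the analysis "once all patients administered AST-VAC2 have withdrawn, died or completed their two-year follow-up visit for survival", so a withdrawn patient counts towards the trigger.
- Protocol 11 lists loss to follow-up and withdrawal of consent as reasons for withdrawal.
- Protocol 7.4.3 lets the sponsor and chief investigator stop survival collection early.
- SAP 7.2 has a row "Completed (2-year OS follow up") and, among the reasons for not completing, loss to follow-up, withdrawal of consent and "Declined to attend follow-up visit".

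In the same SAP, Outcome Measure 3 has an undetermined row and Outcome Measure 5 a not-evaluable row.

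**The concern.** A censored time is a lower bound on survival. If it enters an ordinary median as though it were a death time, an early loss pulls the summary down. If most patients are alive, the summary is set by when they were last contacted. Two programmers could follow this SAP and report different medians from the same data.

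In the two-year tables, a Safety Population member whose status is unknown must be placed as alive, placed as deceased, or dropped from both cells without a rule.

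Two-year OS is a secondary endpoint and is posted as Outcome Measure 6. Protocol 13 also names an increase in OS among the factors for further development. With about eight patients, one patient is enough to change either summary.

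**Working it through.** The plan states no survival figure, loss rate or event target, so there is nothing to reproduce. The sample size of eight comes from Protocol 1.6 and SAP Table 1. All survival times below are assumptions.

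**1. One early loss, n = 8.** Suppose at most three patients are alive at the end, with the longest times, and one other patient is lost at rank *k* among the four shortest. The remaining times up to rank 5 are deaths.

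- Column median = mean of the 4th and 5th ordered times.
- Kaplan-Meier after rank 4: S = (9−k)/8 × 4/(8−k).
- Kaplan-Meier after rank 5: S = (9−k)/8 × 3/(8−k).

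| k | S after rank 4 | S after rank 5 |
|---|---|---|
| 1 | 0.571 | 0.429 |
| 2 | 0.583 | 0.438 |
| 3 | 0.600 | 0.450 |
| 4 | 0.625 | 0.469 |

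S passes from above 0.5 to below it at rank 5 without resting on 0.5, so the Kaplan-Meier median is the 5th time whichever tie rule is used. The column median is lower by half the gap between the 4th and 5th times.

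*Illustration:* times 60, 110, 150, 210, 300, 480, 735+ and 800+ days. Column median = (210+300)/2 = 255. If the patient at 60, 110, 150 or 210 is lost rather than dead, the Kaplan-Meier median is 300.

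**2. Where the tie rule matters (same times).** Here S equals exactly 0.5 after day 210.

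| Case | Column | Kaplan-Meier, midpoint to next death | Kaplan-Meier, first time S ≤ 0.5 |
|---|---|---|---|
| No loss | 255 | (210+300)/2 = 255 | 210 |
| Lost at 300 (5th) | 255 | (210+480)/2 = 345 | 210 |
| Lost at 480 (6th) | 255 | (210+300)/2 = 255 | 210 |

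A loss at the 5th rank therefore makes the column median too low only under the midpoint rule. With no early loss and most patients dead, the two medians agree under that rule.

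**3. More than half alive.** Deaths at 60, 210 and 480; contacts at 735, 800, 900, 1000 and 1100. Column median = (735+800)/2 = 767.5. If the same five are contacted 183 days later, it is (918+983)/2 = 950.5. Kaplan-Meier falls to 7/8, 6/8, then 5/8 = 0.625, so the median is not reached either time.

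**4. Two-year table, denominator 8, with 2 alive, 5 dead, 1 unknown.**
- Unknown placed as deceased: 2/8 = 25.0% alive, 6/8 = 75.0% deceased.
- Unknown placed in neither cell: 25.0% alive, 5/8 = 62.5% deceased, and the cells sum to 7.
- Unknown placed as alive: 3/8 = 37.5% alive, 62.5% deceased.

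The possible span in the proportion alive is 12.5 points.

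**The case against.** **The SAP does not prescribe a raw median.** A reader might infer that it does. It does not: 5.9 recognises censoring and 5.10 leaves the method open, so a Kaplan-Meier median would comply. Nor does anything forbid a plus sign on a range limit. This stands. The defect is an unnamed estimator in a shell whose plain reading gives the sample median.

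**The comparison depends on convention.** A reader might conclude that the column median is either too low or exactly right. That is not so under the rule of taking the first time at which S is 0.5 or below, where Kaplan-Meier gives 210 in three of the cases above. The result for losses at ranks 1 to 4 does not depend on the rule. The rest does, so the fix must state one.

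**A majority alive is unlikely.** Protocol 2.1.1 gives 32% one-year survival for lung cancer. If 32% is assumed to apply at two years, the binomial probability of at least 5 of 8 alive is 7.5%. Trial patients may differ, but this case should carry little weight.

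**A figure of 2/7 (28.6%) is not available under the SAP.** Dropping the unknown patient from the denominator departs from the population fixed in 4.1. The title of Outcome Measure 6 also does not invite counting an unknown patient as alive, and Table 15 prints patient numbers, so an unplaced patient would be noticed. These points narrow the problem, but no rule yet places the patient.

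**Losses may be few.** Contacts are scheduled at 3, 6, 9, 12, 15, 18, 21 and 24 months and quarterly thereafter, and Protocol 7.4.3 allows survival to be taken from medical records. This stands; every loss above is hypothetical.

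**No formal analysis is planned** (SAP Table 1 and 7.6). That rules out tests, but a median and a count alive are still reported, and each needs a defined method.

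**Conclusion.** The point holds as a minor defect. The SAP leaves open how median OS is computed from a column of deaths and censored times, and it gives no place to a Safety Population member whose two-year status is unknown.

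With eight patients, at most three alive at the end and one lost among the four shortest times, the column median is below the Kaplan-Meier median under either tie rule. The shortfall is 45 days in the illustration, and its size depends wholly on the assumed times. One unknown patient could move the reported proportion alive between 25.0% and 37.5%.

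The documents do not support saying that survival will be misreported. With vital status complete to two years and most patients dead, the column median equals the midpoint Kaplan-Meier median and Table 15 is exact. Otherwise harm is limited: OS is descriptive, Table 14 shows each patient's time and censoring mark so that a reader can rebuild the curve, and SAP 7.2 reports losses. The exposure is confined to Table 14's summary row and the two-year counts.

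**What to change.** 1. In SAP 5.9 or 5.10, state that median OS is the Kaplan-Meier median, using the midpoint to the next death when S(t) equals 0.5, and shown as not reached where applicable. Keep the per-patient listing and mark a censored range limit with a plus sign.
2. Add a category for status unknown at 2 years to Table 15 and SAP 7.5.6, keeping the full Safety Population as denominator. The example would then read 2/8 alive (25.0%), 5/8 deceased (62.5%), 1/8 unknown (12.5%).
3. State that a patient whose survival collection stopped early under Protocol 7.4.3 is censored at last contact, and is counted as unknown if two-year status is not known.

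The cost is a few sentences of SAP text, one standard SAS procedure and one extra category in two tables. It is descriptive, so it fits the statement that no formal analyses are planned, and trial conduct does not change.
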